The first step in the proposed program of research is to pretest the double-blind, randomized controlled trial procedures and administration of the intervention and data collection procedures to inform the design of a larger randomized controlled trial (RCT). We will also test the feasibility of enrolling participants into a brief, qualitative survey at the end of their pretest participation. This interview will assess caregivers' perspectives on the impact of

COVID-19 pandemic on their child’s health, caregiving and self-care and mimic the recruitment process used in the larger trial. Following completion of the pretest, we will implement a larger double-blind, randomized controlled trial using procedures described below.

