All caregivers enrolled in this study will receive text messages to support scheduling and reminders for follow-up surveys.

All caregivers will complete the baseline survey during the child's index hospitalization and follow-up surveys at the following intervals following the child's discharge:

- 7 days
- one month
- three months
- six months
- 12 months

In between the six month and 12 month survey, we will send caregivers a “check-in” text message reminding them of their 12 month survey and confirming their contact information.

Caregivers will be given the following options for completing the follow-up surveys:

- 1) over the phone during one session,
- 2) over the phone during multiple sessions
- 3) using a web-based survey.

Web-based surveys will be administered using REDCap.

Surveys will elicit self-reported data in the following domains:

caregiver sociodemographic characteristics (e.g., age, race/ethnicity, sex and gender, employment, household composition)

health and healthcare characteristics (e.g., at both the caregiver and child level: health, severity of food insecurity, and nutrition; at the child level: healthcare utilization)

knowledge, attitudes, beliefs and experiences (e.g., caregiver self-efficacy, satisfaction with care, healthcare-related stigma, knowledge of food and other related resource supports)

resource use characteristics (e.g., use of food or other related resource supports, enrollment in SNAP/WIC, contact with Community Resource Navigator).

Additionally, we will access, collect and analyze data from the child’s electronic medical record (EMR) for recruiting and other research purposes, including analysis of healthcare utilization data. The pretest will yield observations to optimize EMR chart abstraction processes. If needed to supplement healthcare utilization data, we will obtain health insurance claims for the child. The informed consent/assent process will inform study participants of the rationale for accessing these data and request participants’ permission to do so.

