CommunityRx-Hunger (CRx-H) Overall Statistical Analysis Plan (SAP)

NCT04171999

March 2, 2018

CommunityRx-Hunger RCT Statistical Design and Power

NIH funding will support a double-blind randomized controlled trial (N=640, 480 food insecure, 160 food secure) and qualitative research to evaluate the impact of CRx-H on adult and child outcomes. This research will fill important gaps in knowledge about how best to intervene in a hospital setting to support food insecure parents or caregivers with a hospitalized child. The study design and analytic plan incorporate best practices to ensure a robust and unbiased approach, drawing on the mixed methods and large scale clinical trials expertise of the multidisciplinary team. The CRx-H trial will be registered on clinicaltrials.gov in accordance with NIH policy. All reporting will comply with CONSORT guidelines. For each aim, we provide hypotheses.

Aim 1: Screening-based interventions target the highest-risk individuals in a population. Food insecurity screening recommended for use in the healthcare setting classifies people dichotomously as food insecure or not. But food insecurity is a dynamic and complex condition and we have found that a child's hospitalization is a triggering event for 19% of previously food secure caregivers. Healthcare systems are moving quickly to adopt a screening-based approach to intervening on food insecurity and other HRSNs, but little is known about what impact this new practice will have on food insecure people. The purpose of Aim 1 is to study the effect of a screening-based approach to delivery of the CRx-H intervention on caregiver self-efficacy and more distal caregiver and child health and healthcare outcomes.

Among caregivers of hospitalized children who screen positive for household food insecurity we will evaluate the longitudinal effects of CRx-H versus usual care on self-efficacy (primary outcome), severity of caregiver and child food insecurity, adult and child nutrition and health, and child healthcare utilization (secondary outcomes).

Hypothesis 1a. The intervention group will report higher levels of self-efficacy at 12 months compared to controls.

Hypothesis 1b. Adults in the intervention group and their children will have a higher rate of food security and nutritious intake at 12 months compared to controls and their children.

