To ensure balance of intervention groups by food security status, we will use stratified randomization to allocate subjects to usual care or CRx-H. Randomization within each strata, immediately after enrollment, will be facilitated by biostatistician [name], using the method of permuted blocks and the uniform random number function in Stata Version 15. A stratum will be closed for enrollment once its accrual goal has been reached.

(1) Usual Care Arm: the usual care arm will receive information in the standard “Caregiver FYI Admissions Packet” from hospital admission staff about all available retail food options in the hospital and the self-serve food pantries operated by Feed1st. In addition to food resources, this packet includes information about visiting hours, parking, hospital amenities, safety restrictions, and patient/caregiver rights and responsibilities. The Feed1st pantries are listed as a food resource for families in need of “free, nutritious food items.” Signage in the Feed1st pantries include information about the Community Resource Navigator (the navigator). Usual care also includes referral to social work according to the discretion of the healthcare team.

(2) CommunityRx-Hunger (CRxH): In this arm of the study, caregivers will receive CRxH in addition to usual care. CRxH will be initiated by the navigator as part of the discharge process and will include: (a) a brief, structured educational intervention about the common problem of food insecurity in households with children and co-occurring needs, like housing, legal and financial assistance, and transportation, (b) delivery and review of a HealtheRx for nearby, vetted resources to address these needs (SNAP/WIC enrollment, food support, services to meet other basic needs), and (c) coaching on how to activate community resources and the community resource navigator, including a series of automated text messages.

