All caregivers randomized to CRxH will receive, in addition to the educational component and review of the HealtheRx, an initial text message (during the discharge process) and can reply “stop” at any time to prevent additional messages. Phone numbers will be verified via text message at the time of 7 day, 30 day, 90 day, 180 day and 12 month surveys and via text message each month in between follow-up surveys. The navigator will respond to text messages within 24 hours during regular work days and within 48 hours of weekends or holidays. The frequency and content of automated text messages sent to caregivers randomized to CRxH will be more frequent in the beginning of the intervention, decrease in frequency between 31-60 days of the intervention, and culminate in a final text at the end of the intervention at 90 days. The content of these messages is based on a text messaging experiment conducted during the the CMMI HCIA CRx study and provides proactive support from the resource navigator. The timing of these messages is informed by the Critical Time Intervention model.

Following randomization, the baseline survey will be administered in the hospital by a research interviewer blinded to the subject’s study arm. All caregivers will have received usual care at the time of the child’s admission and will also be blinded to the arm to which they are randomized. Discharge status of subject’s child will be monitored via the EMR. For caregivers randomized to the intervention, CRx-H will be delivered in the 48 hours pre-discharge. Follow-up surveys will be conducted by telephone using computer-assisted personal interviewing (CAPI) at 7, 30, 90 and 180 days and 12 months post-discharge. To maximize retention, we will use text messaging and phone calls, if needed, monthly between surveys to verify contact information, schedule and remind participants about upcoming surveys.

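### The trial is labelled double-blind, but CRx-H caregivers cannot be assumed blinded once the intervention is delivered, and both primary outcomes are their own reports after that point

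*SAP*

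**What the plan says.** The SAP's opening section (Statistical Design and Power) says that "NIH funding will support a double-blind randomized controlled trial". Protocol B1 of the full-trial version says "we will implement a larger double-blind, randomized controlled trial".

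Detail on blinding appears only in the SAP's Aim 1 methods section. It says "the baseline survey will be administered in the hospital by a research interviewer blinded to the subject’s study arm", and that caregivers, having all had usual care at admission, "will also be blinded to the arm to which they are randomized". Delivery comes afterwards: "For caregivers randomized to the intervention, CRx-H will be delivered in the 48 hours pre-discharge". Neither document says that follow-up interviewers are blinded, or how caregivers stay blinded after delivery.

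CRx-H consists of an educational session, review of a HealtheRx, and "coaching on how to activate community resources and the community resource navigator", with automated texts. In the SAP the texts end at 90 days. Protocol B1 and B2 have an interventionist contact the caregiver to arrange a remote session, and have the HealtheRx sent by text and email and handed over on paper at discharge. Usual care is the standard admissions packet plus discretionary social-work referral (SAP Aim 1; Protocol B7).

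The Aim 1 primary outcome is one self-reported five-point item on confidence in finding community resources, at 12 months. The Aim 2 primary outcome is caregiver-reported satisfaction with discharge, at 7 days. The survey domains in Protocol B2 include "contact with Community Resource Navigator" and resource use.

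**The concern.** Readers take double-blind to mean that neither the person supplying the outcome nor the person collecting it knows the allocation. In this trial the caregiver supplies both primary outcomes, after an intervention that is plain to the person receiving it. A telephone interviewer who hears about navigator contact may also infer the arm.

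Both outcomes are subjective, and both design effects are small: 0.36 points on the self-efficacy item, and a 1.6-point margin on a 0–100 satisfaction score. If the label stands, trial reports will claim protection against response and interviewer bias that the procedures do not give, and both results will be read as stronger evidence than they are.

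**Working it through.** The central check is a comparison of text. The arithmetic that follows is a sensitivity illustration only.

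**1. Who can be regarded as blinded, and when**

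| Time point | Caregiver | Interviewer |
|---|---|---|
| Baseline | Stated blinded (SAP); precedes delivery in both documents | Stated blinded (SAP) |
| Delivery, before discharge | CRx-H arm receives session, HealtheRx and texts; no sham in usual care | Not applicable |
| Day 7 (Aim 2 primary) | CRx-H arm already exposed | No statement |
| 30, 90 and 180 days | CRx-H arm exposed; SAP texts end at 90 days | No statement |
| 12 months (Aim 1 primary) | CRx-H arm exposed earlier | No statement; four earlier surveys may have disclosed navigator contact |

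The documents differ on order: the SAP randomizes before the baseline survey, and Protocol B1 after it. Either way, baseline precedes delivery, so baseline measures are not affected.

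**2. The plan's Aim 1 figure**

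Inputs (SAP, Aim 1 sample size): 3.56 (SD 1.47) vs 3.92 (SD 1.24), power 0.8, α = 0.05, taken as two-sided.

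- Difference = 3.92 − 3.56 = 0.36.
- SD = √((1.47² + 1.24²)/2) = 1.36; standardized difference = 0.265.
- n per arm = 2(1.960 + 0.842)²/0.265² ≈ 224, using unrounded values.
- Dividing by an assumed Mann–Whitney efficiency of 0.955 gives 235, against 236 stated.

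The figure is reproduced to within one and is not in dispute.

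**3. Illustration for Aim 1 (the shifts are assumed)**

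Suppose there is no true effect and a proportion of CRx-H respondents answer one category higher because they know they were helped. The normal approximation is used.

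- SE = √((1.47² + 1.24²)/236) = 0.125.
- 10% move up: shift 0.10, which is 0.10/0.36 = 28% of the design difference. Shift/SE = 0.80, and P(|Z + 0.80| > 1.96) ≈ 0.13.
- 20% move up: shift 0.20, shift/SE = 1.60, probability ≈ 0.36.

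These figures assume that all 236 per arm respond at 12 months. The SAP cites 80% completion at 1 and 3 months, and 71% for all follow-ups, in the predecessor trial. Applied here as an assumption, that leaves 189 or 168 per arm and SEs of 0.140 or 0.149. The probabilities become 10–11% for a shift of 0.10 and 27–30% for 0.20.

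**4. Illustration for Aim 2 (the shifts are assumed)**

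Inputs (SAP, Aim 2 sample size): margin 1.6, SD 8, 320 per arm, so SE = 8√(2/320) = 0.632. The SAP does not give the sidedness of α. One-sided 0.05 requires 310 per arm (620 in total) and fits 640; one-sided 0.025 would require 393 per arm (786).

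Suppose CRx-H is truly worse by exactly 1.6 points and reporting favours it by b points. The chance of falsely declaring non-inferiority at one-sided 0.05 is Φ(b/0.632 − 1.645):

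- b = 0: 5%
- b = 0.4: 16%
- b = 0.8: 35%

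**The case against.** **The SAP sentence may refer to baseline only.** The caregiver statement sits between the baseline survey and delivery, so this is a fair reading. It does not rescue the unqualified double-blind label in either document, because both primary outcomes come later.

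**The contrast between arms is softer than it looks.** All participants get scheduling texts, pantry signage tells every family about the navigator, and nurses routinely share resource information. Usual-care caregivers may well not know their arm, and navigator contact is not exclusive to CRx-H. The consent text is not available, so what caregivers are told about the arms is unknown. All of this stands, but none of it hides a coaching session and a personalised HealtheRx from the person receiving them.

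**Some of the reaction is the intended effect.** Coaching is meant to raise confidence in finding resources, and Aim 2 asks how caregivers respond to openly receiving CRx-H. This stands: only courtesy reporting or interviewer influence counts as bias, and the documents offer no way to separate it from real change.

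**Interviewers may in fact be blinded, and outcome items may already come first.** Both are possible. The documents do not describe follow-up blinding, and the instruments are not included. A reader might infer that follow-up interviewers are known to be unblinded; the documents support only that their blinding is unstated and vulnerable. Equally, relabelling the trial as having blinded interviewers would be unsupported. For self-completed web surveys the question does not arise.

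**Conclusion.** The concern holds as a statement about labelling and interpretation. The documents assert double-blinding, while the procedures give no basis for assuming that CRx-H caregivers are blinded at 7 days or 12 months, and interviewer blinding is stated only at baseline. This rests on the described content of the arms and the timing of the outcomes, and needs no numerical assumption.

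A reader might go further and infer that the Aim 1 false-positive rate is 13% or 36%, or that either primary result would be invalid. The documents do not support that. The shifts are assumed, they must persist to 12 months although the SAP's texts end at 90 days, and no passage gives an estimate of reporting bias. The figures show only that small shifts would matter against design effects of this size.

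Nor would the remedy remove the bias that those figures represent. Caregiver awareness is inherent in the intervention and remains after any relabelling or reordering. What can be gained is an accurate description and less scope for interviewer influence. The change should be made; it does not call for a redesign or a different sample size.

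**What to change.** 1. In the SAP and Protocol B1, replace double-blind with a statement of who is blinded at each time point. Say that caregivers are not blinded after delivery. Describe follow-up interviewers as blinded only if the sponsor confirms that they are kept from the allocation and from earlier answers about the navigator. State the position of the analysts as well.
2. State that self-efficacy and satisfaction are unblinded self-reports, and limit the conclusions accordingly.
3. At every follow-up, by telephone or web, administer and lock the self-efficacy and satisfaction items before any item on the navigator, the HealtheRx or resource use. Where a survey is split over several telephone sessions, put the outcome items in the first.
4. For telephone surveys, have the interviewer record whether the arm became apparent, and report this by arm.

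The cost is revised wording, reordered REDCap modules and one added interviewer item. Keeping earlier navigator answers from later interviewers may need an access restriction or some care in assigning calls. Sample size is unchanged. Any false-positive figures should appear, if at all, only as an illustration under assumed shifts.

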Interviewers will administer telephone-based surveys; self-administration of a web-based follow-up survey will also be offered. We will enroll 660 caregivers (both food secure and food insecure, 20 caregivers enrolled in the pretest and 640 caregivers enrolled in the larger RCT). We will also attempt to enroll the child patient insofar as to view and collect dates of specific doctor’s visits from their electronic medical record. All human subjects will be consecutively screened for inclusion and enrolled as described in Section P. Recruiting Methods. Following screening for eligibility (including food security status), consent and baseline survey collection, participants will be randomized to either usual care or usual care plus the CommunityRx-Hunger intervention using REDCap functionality. Once randomized, an electronic alert will be sent to the Clinical Trials Manager to assign an interventionist. The interventionist will contact the potential participant by phone or text to schedule a time to deliver the CommunityRx-Hunger intervention remotely via web-conferencing technology (e.g., Zoom, FaceTime) on their personal cell phone or an iPad or tablet. If an iPad or tablet is needed, researchers in the [name] Laboratory will communicate with staff members in Child Life Services (CLS) to deliver iPads/tablets to the caregiver in the hospital, and provide a brief training on how to use the iPad/tablet and get connected to the web-based conferencing technology. Researchers in the [name] Lab will also print a hard copy HealtheRx to networked printers in the CLS offices; Specialists will place this hard copy HealtheRx in the patient’s paper chart for delivery at discharge. Child Life Services sees every child in the hospital as part of their usual daily operations and provides iPads/tablets to patients for their use. A letter of support from [name], MS, Director of Child Life Services, describing their engagement in this study, is enclosed with this protocol. Usual care is described below in Section G. Use of Controls or Placebos.

B2. CommunityRx-Hunger (CRx-H) Intervention

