The main analyses will follow the principle of intent-to-treat, and include all 480 food insecure caregivers in the study arm to which they were allocated. We aim to minimize missing data by employing interviewer-administered surveys and communicating to participants the protections of a certificate of confidentiality. Using these strategies, item non-response ranged from 0-3% in our CRx trial. To avoid potential bias due to missing data, analyses will be conducted using multiple imputation with the chained equations method or inverse probability weighting to account for dropout and/or item non-response. In addition, characteristics of caregivers who complete each interview will be compared to caregivers who do not.

To fully leverage the longitudinal data, generalized linear mixed-effects models (GLMM) will be fit with particular interest in the time (baseline and 7, 30, 90 and 180 days and 12 months post-discharge) by study arm interaction. Based on this model, appropriate contrasts to test the intervention effect at specific time points (e.g., 12 months) will be constructed. These contrasts will permit examination of early versus late effects of the intervention, valuable information for future iterations of this and other parent/caregiver self- and family management interventions. GLMM can be used for continuous (e.g., food security score, amount of fruits and vegetables per day), ordinal (e.g., caregiver self-efficacy, food insecurity categories), or binary (e.g., enrollment in SNAP/WIC) outcomes. If there is a serious imbalance in baseline covariates despite randomization, those covariates will be included in the model. Latent growth curve modeling is a viable alternative to GLMM and will be explored when sufficient variability in the distributions of patterns of outcomes by time points exist (e.g., with the binary outcomes there will be a limited number of potential patterns).

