We will also use survival analysis methods and methods for analyzing count data (e.g., Poisson or negative binomial regression) to assess the following secondary outcomes among children: 1) time to child follow-up for the post-discharge medical visit, 2) time to and number of ER visits, 3) time to and total days of hospitalization. For example, time from discharge to first ER visit will be calculated for each subject and those who never have an ER visit will be censored at the end of study follow-up. Stratified Cox proportional hazards regression models will be fit with intervention group as the independent variable and discharge location (e.g. transplant unit, general unit) as a stratification factor, due to the potential for different underlying rates based on discharge location. The proportional hazards assumption will be checked using log-log plots of survival and Schoenfeld residuals.

For the primary outcome (self-efficacy for self-care at 12 months) a sample of 236 caregivers per arm allows for detection of an intervention group difference of similar magnitude as that found in our CRx trial (3.56 +/- 1.47 vs. 3.92 +/- 1.24). Calculations were performed under the following conditions: with nonparametric adjustment accounting for the fact that an ordinal logistic model with intervention group as the only covariate is equivalent to a Mann-Whitney U test; sample size calculation using a group allocation of 1:1; power=0.8; $\alpha=0.05$. We will therefore enroll 480 food insecure caregivers to accomplish Aim 1. With this sample size, power is sufficient to see at least a 0.26 standard deviation (SD) difference in Generalized Self-Efficacy between intervention and control groups. Assuming a standard deviation of about 5 (based on US adult population norms), a 0.26 SD difference would be equal to 1.3 points.

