We will use the analytic approach described for Aim 1, following the principles of intent-to-treat. Here, we discuss analytic issues unique to Aim 2. To facilitate ease of interpretation of the primary outcome, we will linearly rescale the composite score for the Child HCAHPS dimension of satisfaction with discharge.⁵⁹ Three possible responses for each of the five items included in this dimension will be scored as: No=1; Yes, somewhat=2; Yes, definitely=3. Scores will be transformed using the formula: $y = 100 * (x-a)/(b-a)$ where y=the transformed score, x=the original score, a=the minimum possible score and b=the maximum possible score. Transformed items will be averaged to generate the composite score (range 0-100, higher values mean greater satisfaction). Of particular interest for the non-inferiority hypothesis (H2a) will be the confidence interval for the difference (usual care - CRx-H) and whether or not the upper limit of the confidence interval exceeds the non-inferiority margin. Of note, superiority of the intervention with respect to satisfaction with care, child and caregiver health, and stigma will also be tested as this can be done without penalty. Caregiver satisfaction will be measured at 7 days post discharge and will reference the index hospitalization; no longitudinal analyses will be conducted for this outcome. Typically, analyses of HCAHPS data adjust for case-mix (age, education and general health status); this will be feasible, but given the randomized design and single-site analysis, adjustment should not necessary. To determine whether there are substantial differences in the intervention's effect on food insecure compared to food secure caregivers, the intervention by food security status interaction will be tested. As in Aim 1, we will examine for differential intervention effects on primary and secondary outcomes among racial and ethnic groups, and by sex, using effect modification analyses. Some analyses will be restricted to the food secure group (N=160) to provide a more complete assessment of the impact of the intervention on this group (e.g., changes in knowledge and attitudes about food insecurity and changes in food security over time).

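### The Aim 1 primary model adjusts only after an undefined serious imbalance and uses baseline self-efficacy only as a time level, so the 12-month contrast forgoes available precision.

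*SAP*

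**What the plan says.** In the SAP, Aim 1, Analysis and Sample Size Justification, the longitudinal outcomes are analysed with generalized linear mixed models. Baseline and the five follow-ups are the levels of time, and interest lies in the time-by-arm interaction. From this model "appropriate contrasts to test the intervention effect at specific time points (e.g., 12 months) will be constructed". The covariate rule is "If there is a serious imbalance in baseline covariates despite randomization, those covariates will be included in the model". No threshold, candidate list or decision-maker is given. Nothing in the SAP or in the protocol's Statistical Plan (section C of the full-trial protocol) names baseline self-efficacy as a covariate or constrains the arms to a common baseline mean.

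Hypothesis 1a is about a level: "The intervention group will report higher levels of self-efficacy at 12 months compared to controls". The sample size rests on "an ordinal logistic model with intervention group as the only covariate". Self-efficacy is listed among the baseline survey domains.

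On randomisation, the SAP says "To ensure balance of intervention groups by food security status, we will use stratified randomization". For Aim 2 it says "the intervention by food security status interaction will be tested", but it does not say that food security status is a main effect in the non-inferiority model.

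The documents disagree on when baseline is taken. SAP, RCT Strategy: "Following randomization, the baseline survey will be administered in the hospital by a research interviewer". Protocol, B1 Introduction, after eligibility screening: "consent and baseline survey collection, participants will be randomized to either usual care or usual care plus the CommunityRx-Hunger intervention".

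**The concern.** There are two linked weaknesses in the primary model.

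- **The trigger is undefined.** Whether to adjust, and for what, is settled after the data are seen. Under randomisation an observed imbalance is chance. The better reason to adjust is that a covariate predicts the outcome, and that can be named in advance.
- **The strongest obvious predictor is not used for precision.** The same item measured at baseline is available, yet as a level of time with free arm means it does not sharpen a 12-month level comparison when data are complete.

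What is at stake is power. The trial enrols 480 food insecure caregivers against a requirement of 2 × 236 = 472, so it has little margin on a 12-month endpoint.

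In Aim 2, balancing on a stratum and then leaving it out of the model makes the confidence interval slightly too wide. That is conservative for non-inferiority.

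**Working it through.** **Inputs from the SAP.** Means and SDs 3.56 ± 1.47 and 3.92 ± 1.24; power 0.8; α = 0.05 (sidedness not stated); 1:1 allocation; 236 per arm required and 240 per arm enrolled. For Aim 2: SD 8, margin 1.6, N = 640, of whom 160 (25%) are food secure.

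**Assumed.** The correlation r between baseline and 12-month self-efficacy, taken as 0.3 to 0.6.

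**1. Reproduce the plan's figure.** SD = √((1.47² + 1.24²)/2) = 1.360, so d = 0.36/1.360 = 0.2647. A two-sided t-test at 80% power needs 225 per arm. Dividing by the Mann-Whitney efficiency 3/π = 0.955 gives 235.6, that is 236, which matches. The normal formula gives 224/0.955 = 234.6. A one-sided test gives 186 and does not match, so the plan's test is two-sided.

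**2. What the time-by-arm model does with baseline.** Let f be the variance of the 12-month arm contrast relative to 2σ²/n.

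- Level contrast, free arm means at each time, complete data: f = 1. The fitted means are the observed cell means whatever the correlation. A generalised least squares calculation with six time points and equal correlation gave 1.00 at r = 0.3, 0.5 and 0.7.
- Difference of changes from baseline: f = 2(1 − r).
- Baseline as covariate, or a common baseline mean: f = 1 − r².

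Since 2(1 − r) − (1 − r²) = (1 − r)² ≥ 0, the change contrast is never more precise than adjustment. For r below 0.5 it is worse than ignoring baseline.

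**3. Power.** Power = Φ(d√(0.955n/(2f)) − 1.96). For the raw contrast at n = 240: 0.2647 × √114.6 = 2.834, and Φ(0.874) = 0.809. At n = 236 it is 0.802. For r = 0.5 with baseline as covariate: 2.834/√0.75 = 3.272, and Φ(1.312) = 0.905.

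| r | Raw, 240/arm | Covariate, 240/arm | Change, 240/arm | n/arm for 80%, covariate: 234.6(1 − r²), rounded up |
|---|---|---|---|---|
| 0.3 | 0.809 | 0.844 | 0.668 | 214 |
| 0.4 | 0.809 | 0.871 | 0.735 | 198 |
| 0.5 | 0.809 | 0.905 | 0.809 | 176 |
| 0.6 | 0.809 | 0.943 | 0.887 | 151 |

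**4. Check on the ordinal scale.** A proportional-odds model was fitted to a simulated 5-point item with 240 per arm and 5,000 runs per r. The assumed control probabilities were 0.15/0.12/0.15/0.18/0.40 (mean 3.56, SD 1.48), with intervention mean 3.92. Unadjusted power was 0.790 to 0.796. Adjusted power was 0.821, 0.852, 0.888 and 0.926 for r = 0.3, 0.4, 0.5 and 0.6. Null rejection was 0.043 to 0.052 unadjusted and 0.052 to 0.056 adjusted; the Monte Carlo standard error is √(0.05 × 0.95/5000) ≈ 0.003.

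**5. Sensitivity to dropout.** The SAP reports 80% and 71% survey completion in the earlier CRx trial, that is 192 or 170 per arm. Using those completers only:

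| n/arm | Raw | Covariate, r = 0.3 | Covariate, r = 0.5 |
|---|---|---|---|
| 192 | 0.717 | 0.757 | 0.833 |
| 170 | 0.665 | 0.705 | 0.786 |

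A mixed model recovers some of this loss from earlier visits. With assumed retention falling from 100% to 71% over the six times, the relative variance of the level contrast is 1.346 at r = 0.3 and 1.267 at r = 0.5. With a common baseline mean it is 1.256 and 1.017. Entering these as f at n = 240 gives power of about 0.68 against 0.71 at r = 0.3, and 0.71 against 0.80 at r = 0.5.

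**6. Aim 2.** With 320 per arm the model-based standard error is 8√(2/320) = 0.632. A stratum gap of g SDs at 25% food secure explains 0.25 × 0.75 × g² of the variance. Stratified randomisation already removes that part from the true sampling error. Leaving the stratum out therefore costs only the overstated standard error. For assumed g = 0.2, 0.3 and 0.5 and a true difference of 0, including it gains 0.2, 0.4 and 1.0 power points at one-sided 0.05, and 0.2, 0.6 and 1.6 points at one-sided 0.025. In Aim 1 every participant is food insecure, so no stratum term is missing there.

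**The case against.** The plan never claimed power from adjustment and meets its stated 80% without it, so no error has been shown. That is correct: this is a forgone gain plus one undefined rule.

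The SAP does not write out the model. The appropriate contrast could mean change from baseline, which does use baseline, and a common baseline mean is not ruled out. This is fair as to the text. Hypothesis 1a and the sample-size model point to a level, but they do not settle it. The conclusion survives either reading, because the change contrast is never more precise than adjustment. A common baseline mean would recover the precision, but it has to be stated.

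The main figures assume complete 12-month data and an r that the documents do not supply. This stands. Under dropout all powers fall, and the gain at r = 0.3 is about 3 to 4 points; the large gains need r of 0.5 or more on a single 5-point item. The ordinal check used two time points, not the full repeated-measures ordinal model, and it tested fixed adjustment, not a discretionary trigger.

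The Aim 2 effect is very small. Agreed; it is included because it costs one model term.

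On timing, the SAP blinds interviewer and caregiver at baseline and delivers CRx-H in the 48 hours before discharge. If that is followed, baseline is unaffected by allocation even when taken after randomisation. The two documents still conflict and should agree before baseline becomes a covariate.

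**Conclusion.** The concern holds. The adjustment set of the Aim 1 primary model is not prespecified, and the level contrast that matches Hypothesis 1a gains nothing from baseline self-efficacy when data are complete. At 240 per arm, prespecified baseline adjustment would raise power from 0.81 to between 0.84 and 0.94 for r of 0.3 to 0.6. Put as sample size, 80% power would need about 214 down to 151 per arm in place of 235 by the same normal formula. The gain is modest at r = 0.3 and substantial from 0.5 upwards; r is assumed. The stated 236 per arm is right, and no inflation of type I error is alleged. The Aim 2 omission costs at most 1.6 power points over the stratum gaps tried, and it errs on the conservative side. This should be changed, but it does not invalidate the plan.

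**What to change.** Amend the SAP as follows.

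- **Aim 1.** Delete the imbalance trigger. Define the primary effect as the 12-month arm contrast from the ordinal mixed model for the post-baseline visits, with baseline self-efficacy as a covariate. Alternatively, keep baseline in the outcome vector and constrain both arms to one common baseline mean. Name any further covariates in advance. State that the adjusted odds ratio is conditional on baseline.
- **Aim 2.** Include the food security randomisation stratum as a main effect in the non-inferiority model.
- **Both aims.** Report the unadjusted results as sensitivity analyses.
- **Timing.** Reconcile the SAP and protocol section B1 on whether the baseline survey precedes or follows randomisation, since the adjustment needs a baseline that allocation cannot have affected.

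The cost is wording only, with no new data and no change in sample size. The one small drawback is that the adjusted ordinal odds ratio is conditional, not marginal; the unadjusted analysis kept as sensitivity covers that.
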